2.5 Date scoring & analysis

The results of the experiment were processed using SPSS 26.0. Experimental assistants calculated correct recall and proactive interference rates for each participant's temporal memory.

A mixed-design analysis of variance (ANOVA) was conducted to compare the correct recall rates and proactive interference scores between the two learning strategies under two stimulation conditions. All statistical tests were performed at a significance level of 0.05, and post-hoc comparisons were adjusted using Bonferroni correction. Effect sizes were reported using partial eta-squared (η_p^2 ; ANOVAs).

Study Status

Record Verification: August 2024

Overall Status: Not yet recruiting

Study Start: August 20, 2024 [Anticipated]

Primary Completion: September 30, 2024 [Anticipated]

Study Completion: September 30, 2024 [Anticipated]

List of abbreviations

tDCS transcranial electrical stimulation

L-DLPFC left dorsolateral prefrontal cortex

tDCS transcranial alternating current stimulation

References

- [7] Pastötter B, Weber J, Bäuml K-HT. Using testing to improve learning after severe traumatic brain

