2.1 Participants

Seventy-five inpatients with schizophrenia were recruited from the Third People's Hospital of Lanzhou City (Lanzhou Mental Health Center-Psychiatric Medical Rehabilitation and Nursing Home) and grouped in parallel into 3 conditions, with the sample size depending on the effect size in the study of forward test effects in schizophrenia (Cohen's $d = 1.24$), and to observe a significant level of forward test effects ($\alpha = 0.05$; power = 0.80) a minimum of 11 individuals per group is required [15].

Diagnosis and assessment of patients with schizophrenia were conducted by two chief psychiatrists. Neuropsychological background tests included the Montreal Cognitive Assessment (MoCA) for general cognitive function and the Positive and Negative Syndrome

Scale (PANSS) for symptom assessment.

Inclusion criteria for patients with schizophrenia were: (1) meeting DSM-5 diagnostic criteria for schizophrenia; (2) age \geq 18 years, any gender, education level of primary school or above; (3) all patients receiving stable antipsychotic medication treatment, in a stable phase of illness, able to understand testing requirements, and cooperate to complete all study tasks; (4) no history of neurological or other severe physical diseases, no mental retardation; (5) no color blindness, color weakness, normal vision or corrected vision.

Exclusion criteria were: (1) clear cognitive impairment caused by somatic or cerebral organic lesions, such as cerebrovascular disease, traumatic brain injury, etc.; (2) substance dependence or abuse, mental disorders caused by the use of psychoactive substances; (3) history of brain injury or other central nervous system-related organic diseases; (4) obvious risk of suicide or harm to others; (5) participation in similar experiments within the past 30 days.

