2.2 Design

A between-groups experimental design with 2 (Learning condition: Interim testing, Relearning) \times 3 (Stimulation type: tDCS stimulation, tACS stimulation, sham stimulation) was used. The dependent variables were the final recall accuracy and proactive interference.

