2.3.2 Materials

A chronological memory paradigm from previous research was used [16]. 128 pictures of common objects were selected from a library of standardized color photographs of objects [17] as temporal-sequence learning and testing materials, and a separate practice sequence was set up for subjects to familiarize themselves with the experimental manipulation. According to [18], the picture size was standardized to 350 × 350 (pixels). The 32 sets of sequence pictures were divided into 4 sequences, each of which was a block.

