2.4 Procedure

Before the start of the experiment, the experimenter explained the task and experimental procedure of this experiment, and after the participants understood and agreed to it, they entered the practice phase and started the formal experiment after completion. During this period, participants were informed that after learning each sequence, the computer would randomly decide whether the item order would be tested or not. In fact, whether or not they would be tested was a pseudo-randomized setting, and the test group was tested after learning each sequence. The repeat learning group, on the other hand, was required to learn again. The experimental material was presented on a 14-inch laptop display (resolution 1920 × 1080), with subjects facing the monitor at a distance of about 60 cm, and the screen brightness and contrast were such as to avoid causing discomfort to the subjects.

The classical paradigm incorporating the forward testing effect. Participants first learned the item pictures of the first sequence, displaying the picture items individually in the center of the screen, with each item presented for 2 s. The learning phase required participants to memorize the order of the items that appeared in each sequence, and to press the key to select the order in which the probe items were presented. After the first sequence was learned both groups of subjects solved as many simple math problems as possible within 30s (e.g., $22 + 9 = ?$) . Next, subjects in the temporary test condition were presented with the probe item from Sequence 1, presented for 3 s, followed by the presentation of a combinatorial figure consisting of an array of three objects, and participants were asked to select the object that was presented immediately after it (the target item) from the array of three objects. The setup was the same as in Experiment 1. At the end of the test, learning and testing proceeded with Sequences 2 through 4, with the same process as in Sequence 1.

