The learning process of the repeated learning group was the same as that of the temporary test group, with the difference that the repeated learning group did not have test items in Sequences 1-3, and followed the process of the learning phase to learn the pictures of the items in Sequences 1-3 again, i.e., the order in which the items were presented. The difference is that after learning once in sequence 4, it is no longer necessary to repeat the learning, but to enter the testing phase, which is the same as the setup of sequence 4 in the temporary testing group. The experimental flow is shown in Figure1.

[figure not shown]

Figure 1. Experiment procedure.

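### Section 2.5 states a mixed-design ANOVA over two stimulation conditions, but the design is between-groups with three; MoCA adjustment is a small optional gain once that is corrected

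*Protocol*

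**What the plan says.** - **Analysis (Protocol 2.5).** "A mixed-design analysis of variance (ANOVA) was conducted to compare the correct recall rates" and proactive interference scores. The sentence names two learning strategies and two stimulation conditions. Tests are at 0.05, with Bonferroni correction post hoc. No covariate is named.
- **Design (2.2).** "A between-groups experimental design with 2 (Learning condition: Interim testing, Relearning"), crossed with three stimulation types: tDCS, tACS and sham. There are two dependent variables, final recall accuracy and proactive interference.
- **Participants (2.1).** Seventy-five inpatients, "grouped in parallel into 3 conditions". The sample-size basis is d = 1.24 for the forward test effect, giving a minimum of 11 per group. "Neuropsychological background tests included the Montreal Cognitive Assessment (MoCA) for general cognitive function", alongside PANSS for symptoms.
- **Procedure (2.4).** A testing group and a relearning group are described separately, and "the repeated learning group did not have test items in Sequences 1-3".
- **Hypotheses (1. Introduction).** Testing is expected to beat relearning, and anodal stimulation to beat both tACS and sham.

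**The concern.** The analysis sentence disagrees with the design on two counts. A mixed-design ANOVA needs at least one factor measured repeatedly in the same patient, and section 2.2 has none. Two stimulation conditions leave out one of the three types, and the document does not say which, or whether two are to be pooled. The stimulation hypotheses need all three.

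At stake are the error term for the learning effect, the number of patients in the analysis, and whether both hypothesised stimulation contrasts are tested at all. The trial is listed as not yet recruiting, so the text can still be settled before any outcome is seen.

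A smaller matter follows. Because stimulation is compared between patients, any recall variation that a baseline score predicts stays in the error term. MoCA is such a score and is already listed, but the stated model does not use it.

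**Working it through.** **1. Model against design**

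| Item | 2.2 and 2.4 | 2.5 |
|---|---|---|
| Learning condition | separate groups | one factor of a mixed design |
| Stimulation levels | 3 | 2 |
| Within-patient factor | none described | required by the label |

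Could sequence (1 to 4) be the repeated factor? Not for recall: the relearning group is tested only on Sequence 4, so the two groups share one tested score. Could learning condition be the repeated factor? Section 2.2 calls the design between-groups, and section 2.4 describes one run of four sequences per group, not a second run under the other condition.

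**2. What the choice changes**

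Assume an equal split, which the document does not state: 75/3 = 25 per stimulation type.

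- 2 x 3 between-subjects: 75 - 6 = 69 error df; three pairwise stimulation contrasts, so 0.05/3 = 0.0167 each.
- Learning within patient, three types: 75 - 3 = 72 error df for stimulation, and (75 - 3) x (2 - 1) = 72 within-patient df for learning. Learning is then tested against a different error term.
- Two types, between-subjects: 50 patients, 50 - 4 = 46 error df, and one stimulation contrast where two are hypothesised.

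**3. The protocol's own figure**

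n = 2(1.960 + 0.842)^2 / 1.24^2 = 10.2, rounded up to 11. The minimum of 11 per group reproduces under the normal approximation (t-based: 11.26). It concerns the forward test effect. No sample-size basis is given for the stimulation contrasts.

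**4. The optional covariate**

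Assumptions, none in the document: 25 v 25, allocation unrelated to MoCA, d = 0.8, two-sided 0.0167, and a range for the MoCA-recall correlation r.

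- Unadjusted: noncentrality 0.8/sqrt(2/25) = 2.83, df 69, power 0.646.
- Adjusted: contrast variance multiplied by (1 - r^2)(1 + 1/67), df 68. At r = 0.3 the factor is 0.91 x 1.015 = 0.924, noncentrality 2.94, power 0.687.

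| r | 0 | 0.1 | 0.2 | 0.3 | 0.4 | 0.5 |
|---|---|---|---|---|---|---|
| Power, d = 0.8 | 0.638 | 0.644 | 0.659 | 0.687 | 0.727 | 0.782 |

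Break-even is r = 0.124. At r = 0 the loss is 0.646 - 0.638 = 0.008.

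**5. Scoring noise**

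The r above is the observed correlation. In the test, "participants were asked to select the object that was presented immediately after it (the target item) from the array of three objects", so a score on one final sequence carries binomial noise. Section 2.3.2 says "The 32 sets of sequence pictures were divided into 4 sequences, each of which was a block", which gives 32/4 = 8 sets per sequence, but it also gives 128 pictures, or 32 per sequence. The number of probes is not stated, so k = 8 is only an illustration.

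With mean accuracy p = 0.5-0.7 and true between-patient SD s = 0.10-0.20, both assumed, even a perfect covariate reaches only sqrt(s^2/(s^2 + (p(1-p) - s^2)/k)). That is 0.50 (p = 0.5, s = 0.10) to 0.81 (p = 0.7, s = 0.20).

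| True correlation | Observed r | Change in power, d = 0.8 (points) |
|---|---|---|
| 0.2 | 0.10-0.16 | -0.3 to +0.6 |
| 0.3 | 0.15-0.24 | +0.4 to +2.3 |
| 0.5 | 0.25-0.40 | +2.5 to +8.3 |

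More probes would mean less shrinkage.

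**The case against.** **The mixed label may be intended.** Grouping 75 patients into three parallel conditions fits a design in which only stimulation is between patients and each patient meets both learning conditions. That reading is possible from section 2.1 alone, but sections 2.2 and 2.4 contradict it, and it does not explain the count of two stimulation conditions. What stands is that only the sponsor can confirm the intent.

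**Covariate choice is commonly left to the SAP.** This stands. Naming no covariate is not an error, and section 2.5 does not exclude one. If an SAP already names one, the second part of this point falls away. The gain rests on a correlation the document does not give, and at a modest true correlation even its sign is uncertain.

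**Why MoCA and not PANSS?** The document does not settle this. MoCA is the listed measure of general cognition and the outcomes are cognitive, but the choice is a judgement. No task score is named as an alternative baseline: the learning phase asks patients "to press the key to select the order in which the probe items were presented", but nothing says that this, or the practice phase, is scored.

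**Stronger readings to avoid.** A reader might infer that one stimulation group is to be dropped; nothing says so, and a drafting slip is as likely. A reader might infer that an ANOVA without MoCA is invalid; omitting a covariate does not invalidate it. Nor can the analysis be called sound outright, since the stated model does not match the design and random allocation of patients is not stated.

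**Conclusion.** The mismatch in section 2.5 holds on the text alone and needs no assumption: as written, the model does not fit the between-groups 2 x 3 design and cannot test both hypothesised stimulation contrasts. This is the part that must be corrected.

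The MoCA covariate is a suggestion with a small likely benefit. Before scoring noise is considered, the change at d = 0.8 runs from a loss of 0.8 points (r = 0) to a gain of 13.6 points (r = 0.5; 0.782 - 0.646). With noise on the illustrative 8 probes, a true correlation of 0.3 gains at most 2.3 points. All these figures rest on the equal split, effect size, number of contrasts and correlations assumed above. Chance imbalance in MoCA is part of the same variance and is not a further benefit.

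**What to change.** 1. In section 2.5, state a 2 (learning condition) x 3 (tDCS, tACS, sham) between-subjects ANOVA for both final recall accuracy and proactive interference. This is a wording change only. If the sponsor does intend learning condition to be within-patient, sections 2.2 and 2.4 must be reconciled with that instead, and the stimulation count still corrected to three.
2. Optionally, pre-specify MoCA total score as a single continuous covariate for both outcomes, with the unadjusted ANOVA as a sensitivity analysis. State that MoCA is taken before stimulation; calling it a background test only implies this. The cost is one model term and one error df (69 to 68), and under one power point if MoCA is unrelated to the outcome. No new assessment is needed.

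### The only stated model, a mixed-design ANOVA over two stimulation conditions, does not match the declared between-groups 2 x 3 design

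*Protocol*

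**What the plan says.** Protocol section 2.2 sets out "A between-groups experimental design with 2 (Learning condition: Interim testing, Relearning") crossed with three levels of the second factor ("Stimulation type: tDCS stimulation, tACS stimulation, sham stimulation) was used"). Its outcomes are final recall accuracy and proactive interference.

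Section 2.4 carries this out with a test group and a separate repeat-learning group. The test group is tested after each of Sequences 1 to 4. The repeat-learning group restudies Sequences 1 to 3 without a test and is tested only on Sequence 4. Section 2.3.2 provides one set of material: "The 32 sets of sequence pictures were divided into 4 sequences, each of which was a block".

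The last paragraph of section 1 predicts better accuracy with interim testing than with relearning, and better accuracy with anodal tDCS than with either tACS or sham.

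Section 2.5 then says: "A mixed-design analysis of variance (ANOVA) was conducted", in order to "compare the correct recall rates and proactive interference scores between the two learning strategies under two stimulation conditions". It adds that "post-hoc comparisons were adjusted using Bonferroni correction". No within-subject factor is named.

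Section 2.1 recruits 75 patients, "grouped in parallel into 3 conditions", and states that "a minimum of 11 individuals per group is required".

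**The concern.** A mixed-design ANOVA has at least one between-subject and at least one within-subject factor, and the latter must be observed repeatedly on the same patients. Section 2.2 makes both factors between-groups, so the model in section 2.5 calls for a structure that the design does not have. The same sentence gives stimulation two levels where the design has three.

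What an unseen statistical analysis plan might add does not settle this. The protocol itself fixes a model, and that model disagrees with its own design section. An analyst who followed section 2.5 to the letter would look for a repeated factor that final recall does not supply. The same analyst would also fit a stimulation factor too small for the two stimulation predictions.

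**Working it through.** **1. The plan's own figure.** Section 2.1 gives d = 1.24, alpha 0.05 and power 0.80. Two-sided testing is assumed, since the text does not state sidedness. With the normal approximation:

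n per group = 2(z0.975 + z0.80)² / d² = 2(1.960 + 0.842)² / 1.24² = 15.70 / 1.5376 = 10.2, rounded up to 11.

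The stated 11 is reproduced, so the problem is not one of arithmetic.

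**2. Is there a within-patient factor?** Each candidate in turn:

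| Candidate | What the protocol says | Within-patient? |
|---|---|---|
| Learning | Between-groups (2.2); separate groups (2.4); the four sequences are used up by one learning condition (2.3.2, 2.4) | No |
| Stimulation | Between-groups (2.2); no crossover described | No |
| Sequence | 4 recall tests in the test group, 1 in the relearning group, 1 in common (Sequence 4) | Not for final recall |

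With N patients in g groups and k scores per patient common to all groups, the within-patient error df is (N - g)(k - 1). Here it is (75 - 6)(1 - 1) = 0.

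**3. How many stimulation levels are needed?** Section 2.2 lists three, so df = 3 - 1 = 2. Section 1 states two pairwise predictions (tDCS above tACS, tDCS above sham). A literal two-level factor has 2 - 1 = 1 df:

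- tDCS and sham only: the prediction against tACS is untested.
- tDCS and tACS only: the prediction against sham is untested.
- tACS and sham only, or both active types pooled against sham: neither prediction is tested as stated.

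At least one prediction is lost in every case.

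**4. The model that fits the declared design.** There are 2 x 3 = 6 cells and one final score per patient, 75 scores in all.

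- Learning: 2 - 1 = 1 df
- Stimulation: 3 - 1 = 2 df
- Interaction: 1 x 2 = 2 df
- Error: 75 - 6 = 69 df
- Total: 1 + 2 + 2 + 69 = 74 = 75 - 1

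**5. Does section 2.1 fit?** If its three conditions are the stimulation arms, each has 75/3 = 25 patients, split 12 + 13 by learning condition. Then 3 x 12 + 3 x 13 = 75, and every cell exceeds 11 (minimum total 6 x 11 = 66). So it fits.

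**The case against.** The strongest reply is that both conflicts are slips of wording. Sections 2.2 and 2.4 describe the design clearly. With no repeated factor available, the analyst would end up with the 2 x 3 between-subjects ANOVA, and a wrong label by itself changes no estimate. The word two may be a slip for three, or may echo section 1, which speaks of two stimuli (tDCS and tACS), with sham as the control. On either reading both stimulation predictions can be tested. Much of this stands, and it limits the consequence. It does not remove the point, because the sentence that defines the only stated model should not have to be corrected by inference.

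A second reply is that repeated responses may exist. Section 2.4 mentions a key press in the learning phase, proactive interference is not defined in the text, and the procedure figure is not available here. This is fair, so the claim of no within-patient factor is made for final recall. It does not rescue the mixed label, since section 2.2 declares no repeated factor for either outcome.

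Three stronger readings are tempting, and the documents do not support them:

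- **Section 2.1 contradicts the six-cell design.** It would do so only if the three conditions were the complete set of groups, which the section does not say. Read as stimulation arms, they agree with section 2.2.
- **The group structure cannot be determined, or the trial cannot be analysed.** The between-groups structure is readable from sections 2.2 and 2.4.
- **The conflict does measurable damage to degrees of freedom or sample size.** Three groups with learning varied within patients would have error df of 75 - 3 = 72 instead of 69, a negligible change. The 75 patients exceed the stated minimum under six groups (66) or three (3 x 11 = 33).

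**Conclusion.** The point holds as two errors in the model sentence of section 2.5. The mixed-design label contradicts a design with both factors between-groups, and final recall offers one common score per patient, hence 0 within-patient error df. The count of two stimulation conditions contradicts the three listed in section 2.2. If it were followed literally, the factor would have 1 df instead of 2 and at least one of the two stimulation predictions would go untested. That loss is conditional, since two is probably a slip.

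The conclusion assumes that sections 2.2 and 2.4 describe the intended design. If learning was meant to vary within patients, the mixed label would be right and those sections wrong, so the documents need correction either way. The point should be fixed, but it is a repair of wording: no bias and no shortfall in sample size is shown.

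**What to change.** In section 2.5, replace the model sentence with:

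> For each outcome, a 2 (learning: interim testing, relearning) x 3 (stimulation: tDCS, tACS, sham) between-subjects ANOVA with the interaction will be fitted, including all three stimulation groups. The Bonferroni-adjusted comparisons will include tDCS versus sham and tDCS versus tACS.

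In section 2.1, as a clarification only, say that the three conditions are the stimulation arms, 25 patients each, split 12 and 13 between the two learning conditions.

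If learning was meant to be within-subject, sections 2.2 and 2.4 must be corrected instead, and section 2.3.2 must give the materials for both learning conditions. Section 2.5 must then name the within-subject factor and all three stimulation levels.

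If the declared design stands, the cost is a few sentences, with the same software and no extra patients or data. The protocol gives its status as not yet recruiting, on a record verified in August 2024 with a start anticipated on 20 August 2024. The document cannot show whether outcomes have since been collected. If they have, the correction should be dated and recorded as such.

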This study investigated the effects of an interim test combined with online tDCS and tACS on temporal memory in patients with schizophrenia. Using online tDCS to stimulate the left dorsolateral prefrontal lobe, during which patients learned static visual pictures for temporal memory. Compare the effects of intermediate tests on correct temporal memory in patients with schizophrenia during anodal and sham tDCS and tACS stimulation. It was hypothesized that the pre-test was significantly better than repeated learning for correctness, and that anodal stimuli were significantly more correct than tACS for correctness and false stimuli for correctness.

2. Methods

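### Bonferroni is valid but needlessly conservative for the three pairwise stimulation comparisons; testing them only after a significant stimulation test keeps 5% familywise error with more power

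*Protocol*

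**What the plan says.** - **Error rate and adjustment.** Protocol section 2.5 plans an ANOVA and says "All statistical tests were performed at a significance level of 0.05" and "post-hoc comparisons were adjusted using Bonferroni correction". It does not say how many comparisons form the family or whether they depend on the overall test.
- **Stimulation factor.** Section 2.2 lists "3 (Stimulation type: tDCS stimulation, tACS stimulation, sham stimulation", which is three levels. Section 2.5 describes the comparison as "between the two learning strategies under two stimulation conditions", which is two. These cannot both be right. The three-level reading agrees with sections 1 and 2.1.
- **Hypothesis.** The Introduction expects that "anodal stimuli were significantly more correct than tACS for correctness and false stimuli for correctness". I read this as anodal tDCS above tACS and above sham.
- **Size.** Section 2.1 recruits 75 patients, "grouped in parallel into 3 conditions". Its only power statement concerns the forward testing effect: at d = 1.24, "power = 0.80) a minimum of 11 individuals per group is required".
- **Outcomes.** Section 2.2 says "The dependent variables were the final recall accuracy and proactive interference".

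**The concern.** The stimulation comparisons carry the trial's main scientific claim, yet no power calculation covers them. Bonferroni makes each one harder to pass. That price is worth paying when it buys error control that nothing cheaper provides. For three groups something cheaper exists. If any two of the three pairwise equalities hold, the third follows, so every intersection of pairwise null hypotheses is the global null. The overall stimulation test in the planned ANOVA already tests that hypothesis. Requiring it to be significant at 0.05 before testing any pair at 0.05 is therefore a closed test, and it controls the familywise error at 5% whichever pairs are truly equal. What is at stake is a lower chance of confirming a real stimulation effect with the same patients.

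**Working it through.** **The plan's own figure.** Two-sided normal approximation for two means with d = 1.24, alpha 0.05 and power 0.80:

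n = 2(1.960 + 0.842)² / 1.24² = 15.70 / 1.5376 = 10.2, rounded up to 11 per group.

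This reproduces the protocol. The two-sided t test needs 12 (power 79.0% at 11, 82.7% at 12). The calculation concerns the testing effect and says nothing about stimulation.

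**Inputs for the comparison**
- Alpha 0.05 (section 2.5), taken as two-sided because the protocol does not say.
- Three stimulation levels (section 2.2), so 3 × 2 / 2 = 3 pairs and a Bonferroni level of 0.05/3 = 0.0167. The count of three is inferred from the design.
- 75/3 = 25 per level, assuming an equal split. Error degrees of freedom are 75 − 3 = 72, or 75 − 6 = 69 if the six cells are all between patients. The results hardly differ.
- Stimulation effect: not given, so assumed at d = 0.5 to 1.24 with tACS equal to sham.

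**Method.** Simulation of three normal groups with pooled error variance. Bonferroni rejects a pair if p < 0.0167. The gated procedure rejects a pair if the overall F has p < 0.05 and the pair has p < 0.05.

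**Chance of showing anodal better than both tACS and sham, 25 per level**

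| d | Bonferroni | Gated, pooled variance | Gain |
|---|---|---|---|
| 0.5 | 0.126 | 0.245 | 0.119 |
| 0.8 | 0.496 | 0.677 | 0.181 |
| 1.0 | 0.770 | 0.888 | 0.118 |
| 1.24 | 0.948 | 0.983 | 0.035 |

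Welch versions of both steps give 0.664 at d = 0.8 and about 0.88 at d = 1.0. Holm alone gives 0.563 at d = 0.8. With a graded effect (anodal 1.24, tACS 0.62, sham 0) the figures are 0.40 for Bonferroni and 0.58 gated.

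A single comparison, anodal against tACS, also gains: 0.647 to 0.750 at d = 0.8. The point therefore does not depend on reading the hypothesis as requiring both.

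**Familywise error, equal variances**

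| True state | Bonferroni | Gated | Unadjusted, no gate |
|---|---|---|---|
| All three equal | 0.043 | 0.050 | 0.121 |
| tACS = sham, anodal far away | 0.017 | 0.050 | 0.050 |

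**Familywise error, unequal variances** (25 per level, tACS = sham, anodal shifted by 2 units; the SDs are assumptions)

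| Anodal SD relative to the others | Bonferroni, pooled | Gated, pooled | Gated, Welch |
|---|---|---|---|
| 0.7 | 0.029 | 0.074 | about 0.050 |
| 0.5 | 0.038 | 0.088 | about 0.050 |

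**The case against.** The strongest reply is that nothing here is wrong. Bonferroni after an ANOVA is valid, and choosing another valid method may be only a matter of taste. The first part stands. A reader might infer that the plan has an error-rate fault, and the documents do not support that: within this family Bonferroni keeps the error at or below 5%.

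A reader might also infer that Bonferroni buys nothing. That is too strong as well. Its slack absorbs unequal variances, where the pooled gated procedure reaches 7 to 9%. Recall accuracy is a bounded rate from a three-object choice, so equal variances cannot be assumed. Welch versions restore about 5% and keep nearly all the power, so this limits how the change is made without removing its benefit.

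Three further limits stand:
- **The family is inferred.** Section 2.5 gives no number of comparisons and names two stimulation conditions. The 0.0167 level follows from section 2.2 and is not stated in the plan.
- **The scope is narrow.** The result covers the stimulation main effect for one outcome. It does not cover all comparisons among the six cells, stimulation comparisons repeated within both learning conditions, or error across the two outcomes. The title and the Introduction also point to stimulation combined with interim testing, for which those other comparisons may matter as much.
- **The size is assumed.** At d = 0.5 both methods usually fail, so the sample is the main constraint there. At d = 1.24 the gain is small, although that value describes the testing effect.

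**Conclusion.** The point holds as an efficiency improvement. For the three pairwise comparisons of the stimulation main effect, Bonferroni is valid but more conservative than it needs to be. A gated procedure keeps familywise error at 5% per outcome and raises the chance of showing anodal better than both comparators by roughly 11 to 18 points for d between 0.5 and 1.0, and by about 3 points at d = 1.24. This rests on an equal split of 25 per level, tACS equal to sham, two-sided tests, three stimulation levels, an enforced gate, and either equal variances or Welch tests. The label is cheap improvement.

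**What to change.** In section 2.5:
1. Reconcile the number of stimulation conditions with section 2.2.
2. For each outcome, test the stimulation factor at 0.05. Only if it is significant, test each of the three pairwise stimulation comparisons at 0.05. State that no pairwise result is claimed otherwise.
3. Use Welch versions of both the overall and the pairwise tests where variances are unequal.
4. For comparisons among the six cells, or stimulation comparisons made within the learning conditions, use Holm in place of Bonferroni.

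The SPSS LSD option supplies only the unadjusted pairwise tests. The analyst must apply the gate, because without it familywise error is about 12% when all three levels are equal.

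The cost is a few sentences and no extra patients. Section 2.5 lists the trial as not yet recruiting, so on that status the change can be made before any data exist. There are two downsides: simultaneous confidence intervals will no longer match the tests, and Bonferroni's slack against unequal variances is lost unless Welch tests are used.
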